### 7.2.2 Nasopharyngeal Swabs:

The examiner will:

1. Place an adult flocked swab with a nylon tip through the right nostril and down the nasopharynx of each participant. Note that if the swab is not perpendicular to the frontal plane of the face, it is likely not in the inferior turbinate.
2. Once you reach the nasopharynx, rotate the swab 180° as you remove the swab from the nose.
3. Place the swab in a tube containing 1.0 mL DNA/RNA shield media by Zymo media, cut the handle off using sterile scissors, and close the cap of the tube with the swab immersed.
4. Place study number label on the collection tube and then store at -80C until processing.

Do not attempt to collect the NP swab if you are not successful after **three** attempts.

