#### **7.2.2 Nasopharyngeal Swabs:**

The examiner will:

1. Place an adult flocked swab with a nylon tip through the right nostril and down the nasopharynx of each participant. Note that if the swab is not perpendicular to the frontal plane of the face, it is likely not in the inferior turbinate.
2. Once you reach the nasopharynx, rotate the swab 180° as you remove the swab from the nose.
3. Place the swab in a tube containing 1.0 mL DNA/RNA shield media by Zymo media, cut the handle off using sterile scissors, and close the cap of the tube with the swab immersed.
4. Place study number label on the collection tube and then store at -80C until processing.

Do not attempt to collect the NP swab if you are not successful after **three** attempts.

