#### **Inclusion Criteria:**

1. Over 18 years of age
2. Undergoing cataract surgeries that would benefit from intracameral antibiotics
3. Able to provide swabs
4. Able to provide consent
5. Surgery of the second eye occurs at least 8 weeks after surgery of the first eye

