## **Chapter 7: Specimen Collection for Resistance and Microbiome Testing**

### **7.1 Participants**

We will collect nasopharyngeal, conjunctival, buccal, and rectal swab samples from all 108 participants. The swabbing will occur prior to surgery (conjunctival), 1-week post-op (conjunctival, NP, buccal, rectal), and 4-Week post-op (conjunctival, NP, buccal). The enrolled participants will be given instructions on when and where to go for swabbing visits after surgery.

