#### **7.2.1 Conjunctival Swabs:**

The examiner will:

1. Have the patient sit or lay on a chair with their head well supported. The chair will be adjusted to the appropriate height to ensure the patient's safety.
2. Each individual will use new bottle of proparacaine eyedrop for local anesthesia before taking conjunctival sample. Instruct the patient to look up and expose the conjunctiva by gently pulling down the lower lid of the surgical eye. Gently sweep the conjunctival swab along the lower fornix from inner to outer canthus without touching the eyelids.
3. Place each swab in a separate tube containing 2.0 mL DNA/RNA shield media by Zymo, break it off at its natural break-off point, and close the cap of the tube with the swab immersed.
4. Place study number label on the collection tube and then store at -80C until processing.

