### 7.2.3 Buccal Swabs:

The examiner will:

1. Have the patient rinse mouth with water prior to sample collection
2. Instruct the patient to open their mouth and insert the buccal swab into one side of their mouth, between the cheek and upper gum. Press firmly and twirl swab against the inside of their inner cheek and over the gums for at least 30 seconds using an up/down and front/back motion on each side (1 minute total for both sides). Hold the swab as close to its head as is

comfortable for the patient. While you rub the cotton swab, turn the plastic shaft. This will ensure the entire tip is covered with cells from the cheek. This sampling technique should collect buccal cells without drawing blood.

3. Place the swab in a tube containing 2.0 mL DNA/RNA shield media by Zymo, break the swab at its break-off point, and close the cap of the tube with the swab immersed.
4. Place study number label on the collection tube and then store at -80C until processing.

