### **9.4 Catalog Specimens**

We will create a list of study data and specimens, including the age, gender, surgical history, ocular disease history, group participant was in, and symptom questionnaire. We will also list the date of collection and transport, and the storage conditions while in the field and while banked at UCSF. This will facilitate identification of specimens for future analyses.

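### Does swabbing the right nostril in every participant, whichever eye was operated on, spoil the nasopharyngeal result?

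*Combined protocol and SAP*

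**What the plan says.** Both documents give the same rule in section 7.2.2. The combined protocol and SAP says "Place an adult flocked swab with a nylon tip through the right nostril and down the nasopharynx of each participant", and the Protocol also sends the swab "through the right nostril and down the nasopharynx of each participant". The swab is rotated "as you remove the swab from the nose", so it touches the right nasal passage as well as the nasopharynx.

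The neighbouring specimens treat side differently. For the conjunctival swab (7.2.1) the examiner exposes the conjunctiva by "gently pulling down the lower lid of the surgical eye". The buccal swab (7.2.3) is rubbed "on each side (1 minute total for both sides").

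Other relevant text in the combined protocol and SAP:

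- **One operated eye during follow-up.** The inclusion criteria in 4.1 state: "Surgery of the second eye occurs at least 8 weeks after surgery of the first eye". Same-day bilateral surgery is excluded. Nothing restricts entry to right or left eyes.
- **No nasopharyngeal baseline.** Section 7.1: "The swabbing will occur prior to surgery (conjunctival), 1-week post-op (conjunctival, NP, buccal, rectal), and 4-Week post-op (conjunctival, NP, buccal").
- **Specimen list.** Section 9.4 includes age, gender, "surgical history, ocular disease history, group participant was in, and symptom questionnaire". The operated eye is not named.
- **Linkage.** Section 9.1 ties each specimen number to the name, medical record number and surgical history. The study coordinator and the biostatistician hold the key.
- **Objectives.** Section 1.2 equates local with the ocular surface and sets a separate systemic objective. It does not assign the nasopharyngeal swab to either.

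The SAP is listed as Appendix 1, but its text is not in the documents reviewed, so the planned nasopharyngeal analysis is unknown.

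**The concern.** The nasopharyngeal swab is the only one-sided specimen not tied to the operated side. Suppose eye drops drain mainly into the nasal passage on their own side. The fixed right nostril then lies on the drainage side for right-eye patients and on the opposite side for left-eye patients, and an overall between-arm difference mixes the two.

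Two misreadings would be possible. A null result could hide a real effect on the drainage side, diluted by left-eye patients. A positive result could be taken as systemic when it reflects only drug running down from the treated eye. With no nasopharyngeal baseline, within-person change cannot help tell these apart.

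**Working it through.** The plan has no nasopharyngeal power figure to reproduce. The only sample-size figure is 36 per arm, and 3 × 36 = 108 agrees with the stated total. Everything below is illustrative.

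**Inputs.** From the documents: 36 per arm. Assumed: two-sided 5% t-test; same-side effect *d* chosen to give 80% power at 36 per arm, which is *d* = 0.670; right-eye share *s*; opposite-side effect equal to a fraction *k* of *d*.

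**1. Dilution under the current rule.** Pooled effect = *d* × [*s* + (1 − *s*) × *k*].

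| Opposite-side fraction *k* | Pooled effect at *s* = 0.5 | Power | Power with 40% / 60% left eyes |
|---|---|---|---|
| 0 | 0.670 × 0.5 = 0.335 | 29% | 39% / 20% |
| 0.5 | 0.670 × 0.75 = 0.502 | 56% | 61% / 50% |
| 1 | 0.670 | 80% | no loss |

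Simulation that includes the extra variance from mixing two kinds of patient gives 27%, 55% and 80% at *s* = 0.5.

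**2. Would another nostril rule separate drainage from a systemic effect?** Take a true systemic effect of zero and a drainage effect of 0.670. The chance of a positive test is:

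| Rule | Drainage fully one-sided (*k* = 0) | Opposite side gets half (*k* = 0.5) |
|---|---|---|
| Right nostril for all (*s* = 0.5) | 29% | 56% |
| Always the operated side | 80% | 80% |
| Always the opposite side | 5% | 29% (effect 0.5 × 0.670 = 0.335) |

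Matching the swab to the operated eye, as the conjunctival swab does, makes this confusion worse. Only the opposite-side rule removes it, and only if drainage is wholly one-sided.

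A binary version agrees. Assume a 10% rate without drops, a 30-point drainage effect and no systemic effect. The right-nostril rule gives a pooled difference of 0.5 × 30 = 15 points and a 39% chance of significance. Operated-side swabbing gives 30 points and 85%.

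**3. What a split by side could deliver.** With half left eyes there are about 36 / 2 = 18 per arm per side.

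- Power within one side at *d* = 0.670 is 50%; 80% power needs *d* = 0.96.
- The 95% interval half-width is 0.68 SD.
- For the side-by-arm difference, SE = √(4/18) = 0.471 SD. Power at 0.670 is 29%, and 80% power needs 1.34.

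**4. Balance between arms.** The right-eye share is equal across arms in expectation. At *s* = 0.5 the SD of the difference between two arms is √(2 × 0.5 × 0.5 / 36) = 0.118. The chance of a gap of at least 20 percentage points is about 8%. That is chance imbalance, not bias.

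**5. Is the operated eye lost?** Section 7.2.1 requires staff to know it at each conjunctival swab. Section 9.1 links specimens to surgical history and the medical record number, and section 9.4 catalogues surgical history. Because the nostril is always the right one, same side or opposite side follows from the operated eye alone.

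**The case for a change.** The strongest case for a change is that it costs almost nothing. One field naming the operated eye and one exploratory table by side would need no extra swabs. Fixing the split before results are known would prevent a choice made after seeing them. The trial sets out to address both local and systemic resistance, yet does not say which the nasopharyngeal swab serves; a stated purpose would tell the examiner which nostril to use. The shared nasopharyngeal cavity may not rescue the design either, because the swab also samples the right nasal passage on the way out.

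Much of this stands as fact. The nostril is not linked to the eye, there is no nasopharyngeal baseline, the specimen list does not name the eye, and under fully one-sided drainage the dilution is real. An explicit eye field and a by-side display would be harmless.

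It does not amount to a needed change. The field is very probably retrievable already. The table is too imprecise to settle the question and would leave the main nasopharyngeal comparison as it is. Re-siting the nostril part-way through would make early and late samples differ, and putting every future swab on one side relative to the eye would end the same-side versus opposite-side contrast on which the table depends.

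**Conclusion.** No change is needed. The harm requires three things together: mainly same-side drainage that persists into a shared cavity, an analysis that pools the sides, and a reading of the nasopharynx as a systemic site. The available text states none of them. If all three held, power for a same-side effect would fall from 80% to between 29% and 56% at half left eyes, and drainage alone could produce a positive test at the same rates. If the sides behave alike, there is no dilution.

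The right-nostril rule is a fair trade-off. Technique is uniform across arms and visits, and the between-arm comparison is unbiased by randomisation. The conjunctival result is unaffected, and section 9.1 places the primary endpoint at week 1 without naming the nasopharynx as primary. The alternatives gain little or reverse the intended benefit. An analyst who wants the by-side view can recover the eye from linked surgical history and report it as exploratory, with its wide intervals. The figures rest on an assumed effect of 0.67 SD, a t-test at two-sided 5%, and 40–60% left eyes.

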### 7.2.3 Buccal Swabs:

The examiner will:

1. Have the patient rinse mouth with water prior to sample collection
2. Instruct the patient to open their mouth and insert the buccal swab into one side of their mouth, between the cheek and upper gum. Press firmly and twirl swab against the inside of their inner cheek and over the gums for at least 30 seconds using an up/down and front/back motion on each side (1 minute total for both sides). Hold the swab as close to its head as is

comfortable for the patient. While you rub the cotton swab, turn the plastic shaft. This will ensure the entire tip is covered with cells from the cheek. This sampling technique should collect buccal cells without drawing blood.

3. Place the swab in a tube containing 2.0 mL DNA/RNA shield media by Zymo, break the swab at its break-off point, and close the cap of the tube with the swab immersed.
4. Place study number label on the collection tube and then store at -80C until processing.

#### **7.2.4 Rectal Swabs:**

The test will require that the participant themselves to obtain a good sample. It is important to describe the test to the participant thoroughly to ensure a good sample is taken. The rectal swabs include an instruction guide (see Appendix) with the following instructions:

1. Put on a clean pair of gloves.
2. Partially open the fecal swab package and remove the top section of the collection vial (this can be discarded).
3. Remove the swab from the package. Take care that the cotton tip is not touched. If it is touched, throw the swab away and begin with a new one.
4. Insert the tip of the swab into your anus only as far as needed to contact fecal material (1-3cm) and rotate 180 degrees. The tip should be a brownish color when removed.
5. Place swab into the preservative in the collection tube. Make sure the swab is fully submerged in the liquid preservative and then break the swab off using the pre-scored breaking point.
6. Screw the cap back on the tube and make sure that it's tightened. Wrap the area where the cap meets the tube with Parafilm to ensure that the sample will not leak, and then place the tube into the appropriate sample box.
7. If the swab cannot be broken off while the tip is fully submerged in the liquid, try twirling the swab in the liquid first (to release the contents of the sample into the preservative) before breaking it off. Avoid rubbing the

sample on the tip of the swab off on the side of the tube where there is no liquid.

8. Hand the tube with the sample to the investigator/study coordinator.
9. The investigator/study coordinator places the number label on the collection tube.
10. Tube will be stored at -80C until sample processing.

### **7.2.5 Materials for Swab Collection for Molecular Testing**

#### **Swabs**

Conjunctival, NP, and buccal specimens will be collected using sterile, individually wrapped adult flocked swabs with a plastic swab shaft (manufactured by Copan or similar manufacturer). Rectal swab specimen will be collected using sterile individually wrapped swab (Zymo Research).

#### **Sample Tubes**

Conjunctival, NP, and buccal samples for molecular testing will be collected into sterile 2.0ml microcentrifuge tubes, manufactured by Sarstedt®. (DNA-free tubes will be used for collection in DNA/RNA shield (Zymo).) Rectal swab specimens will be stored in 2 mL sterile tube with DNA/RNA Shield solution provided as part of the DNA/RNA Shield Collection Tube with Swab (Cat # R1108).

#### **-80°C Freezer**

A dedicated -80°C freezer located at the Heintz laboratory will be available for storage of study samples, including nasopharyngeal, conjunctival, buccal, and rectal swabs.

### **7.2.6 Protocol for Tubing and Handling of Samples**

The tubing and handling protocol must be carefully followed in order to prevent contamination and ensure the safe transport of the samples back to the Heintz laboratory and/or to other institutions for processing. The person in charge of labeling, tubing, arranging, and handling the samples needs to perform this task in the most orderly and attentive manner.

1. Both hands of the tuber should be gloved at all times. The tuber's gloves only need to be changed when any potential contamination of the gloves

occurs. The tuber opens the capped, hinged lid of a microcentrifuge tube, which has been labeled with the participant's random identification number.

2. The investigator/study coordinator should screw the cap of the microcentrifuge tube tightly, flick the tube to mix the sample with the media (for tubes with DNA/RNA shield media), and place it in the sample collection box until transfer to a -80C for storage in the Heintz lab.

All samples will be in sample boxes, labeled with the participant's study number for easy future identification.

## **Chapter 8: Training**

### **8.1 Standardization**

The research team will work together prior to the baseline visit to standardize all study procedures. We will review the format, general logistics, and procedures for all participants. Training and standardization of sample processing will be under the guidance of [name].

## **Chapter 9: Sample Organization, Transport, and Storage**

### **9.1 De-identification**

All specimens will be labeled in the outpatient clinic with a random identification number linked to their name, MR number, and surgical/ocular disease history, but to facilitate masking, only the designated Study Coordinator and the Biostatistician will have access to the key linking the ID with patient information. Age, gender, and surgical/ocular disease history will be available for each specimen, but names will be kept confidential. Therefore, all specimens will be de-identified. Please note that the Study Coordinator who is unmasked to the study arms will not be collecting samples at 1-week post-op (primary endpoint) to prevent potential biases.

### **9.2 Specimen Transport**

ARIES Study

Manual of Operations and Procedures

After sample collection, samples from the clinic will be transported to the Heintz laboratory for storage and processing.

### **9.3 Specimen Storage**

Sample storage will occur in two stages: short-term and long-term.

#### **9.3.1 Short-term Sample Storage**

Samples will be labeled with study ID only and are unidentifiable without access to the study database. All samples will be transported to the Heintz laboratory for storage and processing.

#### **9.3.2 Long-term Sample Storage**

All samples processed by the Heintz laboratory will be stored in the -80°C freezer for at least 5 years.

### **9.4 Catalog Specimens**

We will create a list of study data and specimens, including the age, gender, surgical history, ocular disease history, group participant was in, and symptom questionnaire. We will also list the date of collection and transport, and the storage conditions while in the field and while banked at UCSF. This will facilitate identification of specimens for future analyses.

## **Chapter 10: Study Medication**

All adult participants over 18 years of age will be given moxifloxacin intracamerally during surgery. Depending on which group the participant is assigned to, the participants may also be instructed to take topical moxifloxacin at home.

We will monitor as described in the adverse events section. The treatment and monitoring schedule for all study arms is shown in Table 1.

### **10.1 Study Medication Description**

#### **Moxifloxacin**

Will be purchased by the subjects

### **10.2 Dosage Information**

Moxifloxacin will be administered intracamerally during surgery for all participants. The study doctor will use a different moxifloxacin vial for each participant.

All participants in Group 2 and Group 3 will also be taking topical moxifloxacin eye drops at home.

- Group 2: 4 times a day
- Group 3: once a day

Individuals who are allergic to fluoroquinolones will not be in the study.

### **10.3 Medication Procurement/Donation**

None.

### **10.4 Medication Quality Control**

Intracameral moxifloxacin will be obtained through UCSF pharmacy in compliance with UCSF policy. Topical antibiotics will be dispensed as prescribed. All topical medications are FDA approved.

### **10.5 Adverse Reactions/Side Effects**

Moxifloxacin is generally well-tolerated. The most common side effects of moxifloxacin are diarrhea, nausea, dizziness, and headache, each of which may occur as likely as 4% when taking orally and 8% while taking intravenously. Rarer side effects include dysphagia and stomatitis. Diarrhea due to *Clostridium difficile* has been reported in rare cases.

During the consent process, the common adverse reactions that may occur will be explained to the participant and they will be advised to communicate adverse events to UCSF study staff immediately. If, for any reason, the participant needs further care, they will be referred to the nearest health center for examination and treatment.

The trial sites will be masked to molecular outcomes. There will be no interim analysis given that this is a small study. Statistical monitoring is discussed in the Statistical Analysis Plan. The Data Safety and Monitoring Committee (DSMC)

will be given authority to discontinue treatments at any time if there is evidence of unexpected harm.

## **10.6 Adverse Events Systems**

Both active and passive monitoring systems for adverse events are in place for this study. We will monitor adverse events at 1-Day post-op, 1-Week post-op, and 4-Week post-op.

### **10.6.1 Passive Adverse Events Monitoring**

We will implement a passive monitoring system during the study, by instructing patients to report any adverse events during the study period. Patients will be referred for follow-up care on a case-by-case basis.

### **10.6.2 Active Adverse Events Monitoring**

#### **Ocular Symptoms/Quality Survey**

To identify any adverse events during the study, the research team will administer the survey (DEQ-5 and SPEED questionnaires) to each participant at 1-day, 1-week, and 4-weeks after surgery. This survey will be completed by the participants themselves before specimen collection.

#### **10.6.3 Adverse Events Data**

We will keep records and report all potential adverse events to the DSMC. Reporting of non-serious and serious adverse events will follow UCSF IRB procedures.

## **Chapter 11: Protection of Human Subjects**

Study staff will proceed only if participants consent to participate. To be able to collect specimens, we will obtain written informed consent from the participant. This written consent will contain information regarding all study activities with patient contact. We will collect one written consent form for each patient the first time we enroll them. The subsequent visits we will explain the study to the participant, but we will only obtain verbal consent. If, at any time, the participant elects to withdraw themselves from the study, they will be free to do so.

Individuals who withdraw will be offered the same medical treatment outside the study.

### **11.1      Institutional Review Board Approval**

#### **UCSF Committee on Human Research**

UCSF's Committee on Human Research will annually review study protocol for ethical approval.

### **11.2      Written Consent**

Each participant will be asked to sign the written consent form if they agree to be included in the study.

